11.2.4 Expectedness

A serious adverse event that is not included in the Adverse Reaction Section of the relevant Reference Safety Information (RSI) by its specificity, severity or outcome is considered an unexpected adverse event. The reference safety information for this study are the respective sections of the IB of Pembrolizumab and of the SmPC of Rituximab. For the purpose of SUSAR reporting, the version of the IB in force at the time of occurrence of the SUSAR applies.

11.2.5 Duration

For both AEs and SAEs, the Investigator will maintain a record of the start and stop dates of the event.

11.2.6 Action Taken

The Investigator will report the action taken with IMP as a result of an AE or SAE, as applicable (e.g., discontinuation or reduction of IMP, as appropriate) and report if concomitant and/or additional treatments were given for the event.

11.2.7 Outcome

The investigator will report the outcome of the event for both AEs and SAEs.

All SAEs that have not resolved upon discontinuation of the subject's participation in the study must be followed until recovered, recovered with sequelae, not recovered (death due to another cause) or death (due to the SAE).

11.2.8 Abnormal Laboratory Values

Abnormal laboratory values in laboratory tests that are performed for safety surveillance and are not needed for assessment of any efficacy variables will be captured as adverse events, rather than capturing the raw laboratory values.

An abnormal laboratory value is considered to be an AE if the abnormality:

- results in discontinuation from the study;
- requires treatment, modification/ interruption of IMP dose, or any other therapeutic intervention; or
- is judged to be of significant clinical importance.

Regardless of severity grade, only laboratory abnormalities that fulfill a seriousness criterion need to be documented as a serious adverse event.

If a laboratory abnormality is one component of a diagnosis or syndrome, then only the diagnosis or syndrome should be recorded on the AE page/screen of the eCRF. If the abnormality was not a part of a diagnosis or syndrome, then the abnormal laboratory value should be recorded as the AE.

11.3 Definition of an Overdose of Pembrolizumab for this Protocol and Reporting of Overdose

For purposes of this study, an overdose of Pembrolizumab will be defined as any dose of 1,000 mg or greater (≥ 5 times the indicated dose). No specific information is available on the

treatment of overdose of Pembrolizumab. In the event of overdose, the participant should be observed closely for signs of toxicity. Appropriate supportive treatment should be provided if clinically indicated.

If an adverse event(s) is associated with the overdose of a MSD product, the adverse event(s) is reported as a serious adverse event, even if no other seriousness criteria are met.

If a dose of MSD's product meeting the protocol definition of overdose is taken without any associated clinical symptoms or abnormal laboratory results, the overdose is reported as Special Reporting Situation, using the terminology "accidental or intentional overdose without adverse effect."

All reports of overdose with and without an adverse event must be reported within 24 hours to the Sponsor and within 1 working day after becoming aware by the Sponsor to MSD Pharmacovigilance Germany [redacted] [redacted] [redacted] [redacted] [redacted]

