5.4 Safety Variables

Safety variables will include AEs, SAEs, laboratory parameters, ECG and vital signs. The severity of AEs will be graded using the NCI-CTCAE version 5.0 dictionary. An AE is defined as any event arising or worsening after start of study drug administration until 110 days (based on five times the terminal elimination half-life of Rituximab and Pembrolizumab) after the last study drug intake. Safety variables will be summarized by means of descriptive statistics and/or frequency tables as appropriate. All AEs, drug related AEs, serious AEs will be summarized by MedDRA classification and worst CTCAE grade.

[figure not shown]
6. Study Design

This study is a European multicenter, single-arm, open-label, phase II trial of 18 cycles of Pembrolizumab and Rituximab in patients aged ≥ 18 years with previously untreated or relapsed MZL in need of treatment.

The study flow will be as follows:

- Previously untreated or relapsed patients will be screened for eligibility for the trial. If the patient is eligible for the study, the patient will be registered before the first cycle of treatment.
- Patients who progress at any time point during treatment are considered as treatment failure. They will be followed up for overall survival until end of follow up period or death.
- Patients, who achieve at least a SD after treatment will be followed up for response until progression/relapse and for overall survival until death.

Fig.1: Study Design

A multicenter open-label single-arm phase II study

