8.3 Dose adjustments

In general, the following rules should be adhered to:

- In case of several toxicities, the most severe reaction is to be taken for dose reductions.
- Patients must have at least a hemoglobin value ≥ 7.5 g/dL, an ANC $\geq 0.5 \times 10^9/L$, **and** a platelet count $\geq 30 \times 10^9/L$ before continuing treatment.
- Delays of cycles will be done by regimen and not by individual compound.
- Dose reductions will be done by individual compounds as described below.
- If there is the necessity to stop application of single compounds, treatment can be continued omitting the individual drug with the other compounds of the regimen.
- If there is a delay in treatment of > 3 weeks, contact the 'Clinical trials office (Ulm)'.

8.3.1 Pembrolizumab i.v.

8.3.1.1 *Dose Modification and toxicity management for irAEs associated with Pembrolizumab and combination therapy*

AEs associated with Pembrolizumab exposure, including coadministration with additional compounds, may represent an immunologic etiology. These immune-related AEs (irAEs) may occur shortly after the first dose or several months after the last dose of Pembrolizumab/ combination treatment and may affect more than one body system simultaneously. Therefore, early recognition and initiation of treatment is critical to reduce complications. Based on existing clinical study data, most irAEs were reversible and could be managed with interruptions of Pembrolizumab/ combination treatment, administration of corticosteroids and/or other supportive care. For suspected irAEs, ensure adequate evaluation to confirm etiology or exclude other causes. Additional procedures or tests such as bronchoscopy, endoscopy, skin biopsy may be included as part of the evaluation. Based on the severity of irAEs, withhold or permanently discontinue Pembrolizumab and administer corticosteroids.

Dose modification and toxicity management guidelines for irAEs associated with Pembrolizumab/ combination treatment are provided in Table 1.

Attribution of Toxicity:

When study interventions are administered in combination, attribution of an adverse event to a single component is likely to be difficult. Therefore, while the investigator may attribute a toxicity event to the combination, to rituximab alone or to pembrolizumab alone, for adverse events listed in Table 1, both interventions must be held according to the criteria in Table 1.

Holding Study Interventions:

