9.2 Screening procedures

Written informed consent for participation in the study must be obtained before performing any study-specific screening tests or evaluations. Informed Consent Forms for patients who are not subsequently enrolled will be maintained at the study site. Screening tests and evaluations will be performed within 28 days prior to Day 1 of Cycle 1 (defined as the day of the first dose of Rituximab). Results of standard-of-care tests or examinations performed within 14 days prior obtaining informed consent may be used; such tests do not need to be repeated for screening. All screening evaluations must be completed and reviewed to confirm that patients meet all eligibility criteria before initiation of study treatment. Please see the Study Flowcharts provided in Appendix A for schedules of screening and pretreatment assessments.

At the end of the screening period a reference pathology report has to be available before start of treatment.

After the patient signs the study informed consent, any new finding discovered not present in the patient's medical history or a worsening of a prior medical history finding must be recorded as an adverse event. Certain results from diagnostic testing performed as part of the standard of practice prior to the informed consent date and time may be used to fulfill screening criteria. This includes fresh tissue, CT (or MRI) scans, endoscopy with biopsies, bone marrow sample, echocardiogram and hepatitis testing which may be used provided they fall into the protocol specified window (see section 9.1). However, these historical results can only be used after the patient gives informed consent to use them.

The following procedures will be conducted at the Screening visit (after obtaining informed consent):

- Discussion of fertility issues and sperm banking should be performed in patients at childbearing age
- Demographic, Medical History and Ann Arbor Stage
- Complete physical examination, vital signs and ECOG performance status
- Initial staging procedures: iter alia imaging and bone marrow examinations (for details see section 9.1)

- Presence of B–symptoms (fever, weight loss, night sweat)
- 12-lead ECG and Echocardiography
- Laboratory:
 - Hematology
 - Serum chemistry
 - electrophoresis
 - If M protein is present: Serum protein immunofixation
 - Coagulation
 - Thyroid hormones
 - Urine analysis
 - Urine Protein to Creatinine Ratio (UPCR) measurement

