7.6 Variables for Safety Analysis

Safety evaluations include AEs/SAEs/AESIs, clinical laboratory parameters (hematology, serum chemistry, serum immunoglobulin (IgG, IgM, IgA), CRP), and ECG. Laboratory parameters cover parameters of serum chemistry, hematology, quantitative immunoglobulins (IgA, IgG, IgM), and CRP. More details are in the parts 7.1 and 7.2, see above. For ECG, the frequencies of 'Normal or not clinically significant' or 'Clinically significant' will be calculated.

The severity of AEs will be graded using the NCI-CTCAE version 5.0 dictionary. An AE is defined as any event arising or worsening after start of study drug administration until 110 days (based on five times the half-life of Rituximab and Pembrolizumab) after the last study drug intake. All AEs, drug related AEs, serious AEs will be summarized by MedDRA classification (SOC and preferred term) and worst CTCAE grade. Additionally, adverse events of special interest (AESIs) will be analysed as a separate category.

Adverse events (AE), serious adverse events (SAE) adverse events of special interest (AESI): Following variables will be used in the analysis of AEs, SAEs and AESI: *SUBJECTID*, *AESPID*, *AETERM*, *AETOXGR*, *AERELPEM*, *AERELRIT*, *AEACNPEM*, *AEACNRIT*, *AESER*, *AESI*, *AESS*, *AESSCAS*, *AESTDAT*, *AEOUT*, and *AEENDAT* in table *AE*. For the analysis of AEs, the final outcome will be analysed only. AEs, SAEs (variable *AESER* in table *AE*) and AESIs (variable *AESI* in table *AE*) will be analysed separately. Additionally, AEs / SAEs / AESIs of grade ≥ 3 (variable *AETOXGR* in table *AE*) will be analysed separately.

Concomitant medication: Concomitant medication is documented during treatment period. Variables for analysis are *SUBJECTID*, *CMSPID*, *CMTRT*, *CMINDC*, *CMDSTXT*, *CMFREQ*, *CMROUTE*, *CMROUTEOTH*, *CMSTDAT*, *CMONGO*, and *CMENDAT* in table *CM*.

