8.2.6 Safety Analysis

Generally, safety evaluations include: adverse events and clinical laboratory parameters (hematology, serum chemistry, serum immunoglobulin (IgG, IgM, IgA), CRP). The severity of adverse events will be assessed using National Cancer Institute Common Terminology Criteria for Adverse Events, Version 5.0.

Analysis of adverse events (AE), serious adverse events (SAE) and adverse events of special interest (AESI): AEs, SAEs and AESIs will be listed in tabular form. Listings will be provided for all AEs, SAEs, AESIs, and for AEs of grade ≥ 3 , SAEs of grade ≥ 3 , AESIs of grade ≥ 3 . Furthermore, the proportion (incl. 95% confidence interval) of patients with at least one AE / SAE / AESI will be calculated.

Analysis of concomitant medication: The time course of concomitant medication will be provided for each patient as listing of main variables (*SUBJECTID*, *CMSPID*, *CMTRT*, *CMINDC*,

CMDSTXT, *CMFREQ*, *CMROUTE*, *CMROUTEOTH*, *CMSTDAT*, *CMONGO*, and *CMENDAT* in table **CM**) of each medication ordered by number of medication (variable *CMSPID* in table **CM**). **Analysis of clinical laboratory parameter (hematology, serum chemistry, serum immunoglobulin (IgG, IgM, IgA), and CRP):** For each of the parameters of hematology (hemoglobin, hematocrit, platelets, erythrocytes, leukocytes, neutrophils, lymphocytes), serum chemistry (potassium, LDH, ALT, AST, GGT, alkaline phosphatase, uric acid, and CRP), and immunoglobulin (IgA, IgG, IgM) the time course will be analysed descriptively in a separate table with results from descriptive statistics. There will be a separate row for each point in time (see CTP pages 106-110). Furthermore, for each parameter of haematology and serum chemistry the frequency of clinical significant ratings and not clinically significant ratings will be provided.

Analysis of ECG findings: The frequencies for 'Examination performed?' (yes/no) and result (negative/positive) will be calculated for each point in time. In case of a clinically significant result, the time course of the results in the respective patient will be listed (variable *EGORRES* in table **EG**). Additionally, the respective database record in table **MH1** will be listed in this case.

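### All graded safety counts come from the AE table, and no CTCAE grade by itself makes a laboratory value an AE, so severe laboratory values not recorded as AEs are missing from every graded patient-level count

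*Protocol*

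**What the plan says.** **Capture.** Protocol 11.2.8 concerns safety-surveillance tests not needed for any efficacy variable. Abnormal results in these tests "will be captured as adverse events, rather than capturing the raw laboratory values". It then gives three alternative conditions for an abnormal value to be an AE: it results in discontinuation from the study; it "requires treatment, modification/ interruption of IMP dose, or any other therapeutic intervention; or" it "is judged to be of significant clinical importance". None refers to a CTCAE grade.

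**Role of laboratory data.** Protocol 5.4 names them as safety variables in their own right: "Safety variables will include AEs, SAEs, laboratory parameters, ECG and vital signs".

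**Graded outputs.** SAP 7.6 and 8.2.6 apply worst CTCAE grade and the grade 3 or higher analyses to recorded events: "AEs / SAEs / AESIs of grade ≥ 3 (variable *AETOXGR* in table *AE*) will be analysed separately".

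**Laboratory outputs.** For each haematology, chemistry and immunoglobulin parameter, SAP 8.2.6 says "the time course will be analysed descriptively in a separate table with results from descriptive statistics", with one row per time point. It adds the frequency of clinically significant and not significant ratings for haematology and chemistry. Neither document plans CTCAE grading of laboratory values, a worst on-treatment value per patient or a shift from baseline.

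**The concern.** Toxicity is a stated objective in the protocol synopsis and in SAP 2.1, and severity is to be graded by CTCAE v5.0. For laboratory toxicity, a patient enters a graded count only after the investigator in an open-label trial has acted on the value or called it important. The only other laboratory signal with a frequency, the clinical-significance rating, is also ungraded, and nothing indicates that it is made independently of the site. With so few patients, a handful of unrecorded values could noticeably change the reported rate of severe laboratory toxicity, and no planned output would show it.

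**Working it through.** The plan states no figure for this point, so there is nothing to reproduce. The check follows a laboratory value through the two documents.

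1. **From value to AE.** Protocol 11.1.1 includes laboratory values in the AE definition only under specified criteria, which are the three in 11.2.8. A value that meets none of them need not be an AE, whatever its grade.

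2. **From AE to graded count.** SAP 7.6 takes the grade from AETOXGR in the AE table. If no AE was recorded, there is no grade.

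3. **What the visit tables show.** SAP 8.1 prescribes mean, SD, minimum, quartiles, median and maximum. Illustration with assumed platelet values (10⁹/L), where the low values were neither acted on nor judged important:
   - Two of 22 patients at 35 and 20 at 200: mean = (20×200 + 2×35)/22 = 4070/22 = 185; median 200; minimum 35.
   - One of 22 at 35 and 21 at 200: mean = (21×200 + 35)/22 = 4235/22 = 192.5; median 200; minimum 35.

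   The minimum reveals an extreme value, but it is the same in both cases. Across visits, it does not show whether the extremes belong to one patient or several.

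4. **Size.** The denominator is 22 included patients (SAP 2.1), with exact Clopper-Pearson 95% intervals:
   - 0/22 = 0% (0 to 15.4%)
   - 1/22 = 4.5% (0.1 to 22.8%)
   - 2/22 = 9.1% (1.1 to 29.2%)

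   The safety population equals the Core Analysis Population, which excludes withdrawals. At the expected 15%, 22 × 0.85 = 18.7, or about 19 patients (an assumption). One patient is then 1/19 = 5.3 points.

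5. **Parameters covered.** Protocol 9.1.10 lists 27 serum chemistry items by count; SAP 7.1 and 8.2.6 summarise 8 (potassium, LDH, ALT, AST, GGT, alkaline phosphatase, uric acid, CRP). The other 27 − 8 = 19 include creatinine, total bilirubin, glucose, lipase and amylase. They have no serum chemistry summary (albumin appears only as an electrophoresis fraction), so the AE form is their only planned route to a count. The SAP does not say whether their raw values are stored.

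6. **Conversion check before grading.** SAP 12.1 converts leukocytes and platelets from /µL with factor 0.001, but neutrophils from /µL to /nL with factor 1.000. A count of 500/µL should become 500 × 0.001 = 0.5/nL; with the stated factor it becomes 500/nL, 1,000 times too high. Any grade derived from such a record would miss neutropenia.

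**The case against.** The strongest reply is that severe values have several other routes into the AE table.

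- Protocol 8.3 sets blood-count floors for continuing treatment ("Patients must have at least a hemoglobin value" at or above a stated level, with similar limits for neutrophils and platelets). A value below a floor delays dosing and meets the second AE criterion.
- Table 1 in 8.3.1.1 directs withholding or discontinuation for graded liver, renal and other immune-related events.
- Section 8.3.2 allows rituximab delay for neutropenia or thrombocytopenia.
- Section 11.1.2 defines a hepatic AESI by numeric thresholds.
- The third criterion in 11.2.8 makes an important value an AE without any action.

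All of this stands and narrows the gap. It does not close it, because these routes cover selected parameters and situations, and none yields a graded laboratory count independent of AE recording. The display of single values when measurements are few (SAP 8.1) does not yield one either.

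A reader might infer from the capture sentence in 11.2.8 that abnormal values were removed from the raw data and that visit means are biased towards normal. The documents do not support this. SAP section 6 describes stored haematology, immunoglobulin, chemistry and thyroid results, and SAP 7.1 has a significance rating for each haematology and chemistry parameter. The sentence also excludes tests needed for efficacy, which arguably covers haematology: Protocol 9.1.2 uses it for response, and Appendix F requires blood-count recovery for splenic CR. What remains is an unreconciled difference between the 11.2.8 wording and the SAP's description of the database.

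A reader might also see a conflict with Protocol 9.2, where "a worsening of a prior medical history finding must be recorded as an adverse event". That is a general sentence in the screening section; 11.1.1 and 11.2.8 are the specific rules for laboratory values.

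**Conclusion.** The point holds as a gap in the safety analysis. A severe laboratory value that was not recorded as an AE appears in no graded patient-level count, and the planned visit summaries cannot supply one. Each such patient is worth 4.5 points if all 22 are analysed, or 5.3 if 19 are. How many such patients exist cannot be known from the documents; the platelet example is only an illustration. It would be wrong to conclude that every severe value without action goes unrecorded, because investigator judgement and the other routes will capture some. No confirmatory test or efficacy result depends on this. The change is nevertheless worth making, because toxicity is an objective and the stored values allow a check on open-label AE reporting.

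**What to change.** - **SAP 8.2.6:** add a patient-level table of worst post-baseline CTCAE v5.0 grade and shift from baseline, regardless of AE status, derived from stored raw values. Cover hemoglobin, platelets, leukocytes, neutrophils, lymphocytes and potassium, and add ALT, AST, GGT and alkaline phosphatase where site ULNs are available. Report the number of patients at grade 3 or higher.
- **SAP 12.1:** before grading, correct the neutrophil factor from /µL to /nL from 1.000 to 0.001.
- **Before database lock:** query laboratory-term AEs that have no raw value at that visit. This shows whether any site replaced raw values with AE entries.
- **SAP and report:** state whether raw values were captured despite the 11.2.8 wording, and for which parameters the grade cannot be assessed.

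Rewording 11.2.8 would not repair data already collected: the last enrolled patient's end-of-treatment visit was on 06 Dec 2024 (SAP 2.1).

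The cost is one table, some programming and a round of queries. Site ULNs must be obtained for the enzymes, since the SAP names no variable that holds them. Reported laboratory toxicity may look slightly less favourable.

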11.4 Other malignancies

In addition to all routine AE reporting, all new malignant tumors, including solid tumors, skin malignancies and hematologic malignancies, are to be reported for the duration of study treatment and during any protocol-specified follow-up periods including postprogression follow-up for overall survival.

11.5 Pregnancy

Any pregnancy in a female subject or in a female partner of a male subject diagnosed during the treatment period or within 12 months after last study treatment (Rituximab and Pembrolizumab) administration must be reported **immediately** to the Sponsor/ZKS. Follow-up information on the subject and her pregnancy outcome should be communicated by the investigator to the Sponsor as soon as available.

If a participant inadvertently becomes pregnant while on treatment, the participant will be immediately discontinued from study treatment. The investigator should counsel the subject or the partner of the subject, discuss the risks of continuing the pregnancy, and possible effects on the foetus. Monitoring of the patient should continue until up to 8 weeks of age of the newborn. The site will contact the participant at least monthly and document the participant's status until the pregnancy has been completed or terminated.

Pregnancy should be reported on the **Pregnancy Report Form**. If the outcome of the pregnancy meets the criteria for immediate classification as a SAE (i.e., spontaneous or therapeutic abortion, any congenital anomaly [including that in an aborted fetus], stillbirth,

neonatal death), the investigator should follow the procedures for reporting SAEs. All neonatal deaths that occur within 30 days of birth should be reported, without regard to causality, as SAEs. In addition, any infant death after 30 days that the investigator suspects as related to the *in utero* exposure to the study drug should also be reported as SAE.

Such events must be reported within 24 hours to the Sponsor and within 1 working day after becoming aware by the Sponsor to MSD Pharmacovigilance Germany ([REDACTED]).

If a male participant impregnates his female partner, the study personnel at the site must be informed immediately and the pregnancy must be reported to Sponsor within 24 hours. The pregnant female partner should be advised to call their healthcare provider immediately.

